5.2 Test Hypothesis and P-Value Justification

Because of the small sample size and study design, no formal statistical hypotheses will be tested.

5.3 Procedures for Handling Missing Data and Outliers

Missing or incomplete dates will be imputed per Section 6.2.2 for the purposes of determining treatment emergence. All other missing data will not be imputed, unless otherwise noted.

All unscheduled visit data will be included in data listings. In the data summary tables, the presence of missing data will be indicated by the inclusion of a 'missing' category with categorical data, and a count and percentage of missing observations for continuous numeric data, where applicable.

5.4 Interim Analysis

An interim analysis will be planned for September 2018 at the time of Cohorts 1-4 completing the Day 365 Visit and Cohort 5 completing the Day 180 Visit. All TLFs outlined in this SAP will be produced for the interim analysis.

5.5 Subgroup Analysis

Due to the small sample size and the design of the trial, no subgroup analyses will occur.

5.6 Multi-center Studies and Pooling of Centers

This is a multi-center study, but due to the small sample size and the design of the trial, no pooling of centers will occur.

6. STATISTICAL ANALYSIS METHODOLOGY

All data collected for this study will be presented in summary tables, listings, and figures (TLFs) as indicated in Appendix 1 of this SAP. Shells for TLFs with enough detail for programming will be provided as a guide to develop the programming SAS codes. These shells will be in sufficient detail to simulate the actual TLFs when they are created from the locked database.

Tabulations for continuous data will use a standard set of summary statistics: number of observations available (n), mean, standard deviation (SD), median, and range (minimum, maximum).

Categorical or dichotomous data will be tabulated using counts and percentages. The numerator and denominator for each percentage calculation will be specified in the footnotes of table shells.

Data listings will present all information recorded in eCRFs and any derived variable(s) included in the analysis datasets for all subjects and visits.

6.1 Study Subjects

6.1.1 Subject Disposition

Subject disposition will be presented for the Screened Population. The following will be presented in a disposition table:

- Number of subjects screened
- Number of subjects who enrolled but discontinued after DVT prophylaxis was withdrawn and before AST-OPC1 injection (Not Treated Safety Population)
- Number of subjects dosed with AST-OPC1 by cohort and overall (All Treated Population)
- Number and percentage of subjects who terminated prematurely before 1 Year Visit by cohort and overall
- Reason for premature termination before 1 Year Visit by cohort and overall
- Number and percentage of subjects who completed 1 Year Visit by cohort and overall

The number of subjects in the above categories will also be presented in a flow diagram figure.

A table with the number of screen failures and reason for screen failure will be produced.

6.1.2 Protocol Deviations

A protocol deviation is any change, divergence, or departure from the study design or procedure defined in the protocol.

The following categories will be used to group protocol deviations:

- 1. Eligibility not met
- 2. Study Assessment Noncompliance
- 3. Other

The following are categorical reasons used to document why a protocol deviation occurred:

- 1. Subject illness
- 2. Clinical error
- 3. Investigator/staff decision
- 4. Other

A subset of the protocol deviations can be identified as an important protocol deviation as described below:

Important Protocol Deviation: An important protocol deviation that might significantly affect the completeness, accuracy, and/or reliability of the study data or that might significantly affect a subject's rights, safety, or well-being.

At a time prior to the interim analysis and again prior to soft lock of database, all documented protocol deviations in the study will be reviewed to identify all important protocol deviations by a data review team including representatives from clinical operations, medical, data management, and statistics, and sent to the sponsor for approval. Final decisions will be documented and maintained by DPC.

A summary table of protocol deviations will be presented for the number and percentage of subjects in the following categories by cohort and overall:

- ≥1 protocol deviation.
- \ge 1 important protocol deviation
- Important protocol deviation category
- Important protocol deviation reason
- Protocol deviation category
- Protocol deviation reason

6.1.3 **Demographics**

A demographic and baseline characteristics table will be presented for the All Treated Population by cohort and overall. The summary will include descriptive statistics for age, sex, race, ethnicity, weight, height, and BMI at baseline, as well as the AIS grade and cause of spinal cord injury.

6.1.4 Medical and Surgical History

At the Screening visit, the general medical and surgical procedures history will be recorded on the eCRF. Medical/Surgical History data will be summarized by MedDRA version 18.0 System Organ Class (SOC) and Preferred Term (PT).

6.1.5 Concomitant Medications

All prior and concomitant medications, interventions and procedures will be tabulated. Prior and concomitant medications will be coded to the therapeutic drug classes and generic drug names using the World Health Organization Drug (WHODrug) classifications version March 2015.

6.2 Safety Analysis

6.2.1 Exposure

Investigational product exposure and injection day data will be listed, including injection, lumbar puncture, and product label data.

6.2.2 Adverse Events

The collection period for adverse events for the purposes of this protocol begins once the subject has signed the informed consent form and ends after 365 days of observation. All adverse events will be listed by subject. The Medical Dictionary for Regulatory Activities (MedDRA) (Version 18) will be used to classify all adverse events by system organ class (SOC) and preferred term (PT).

A treatment emergent adverse event (TEAE) will be considered as any adverse event that starts on or after the date and time of the AST-OPC1 injection, or if an adverse event that started before the AST-OPC1 injection worsened after the administration of the investigational product. For the purposes of determining treatment emergent adverse events, missing or partial AE start dates will be imputed with the following rules:

- 1) If onset date is completely missing, then onset date is set to date of first dose
- 2) If year is present and month and day are missing:
 - a. If year = year of AST-OPC1 dose, then set date to AST-OPC1 dose date
 - b. If year < year of AST-OPC1 dose and medication AE end month and year are available, then set to first of the AE end month
 - c. Otherwise if year < year of AST-OPC1 dose, then set month and day to December 31st.
 - d. If year > year of AST-OPC1 dose, then set month and day to January 1st.
- 3) If month and year are present and day is missing:
 - a. If year = year of AST-OPC1 dose and
 - i. If month = month of AST-OPC1 dose then set day to day of AST-OPC1 dose date

- ii. If month \neq month of AST-OPC1 dose then set day to first day of month
- b. If year \neq year of AST-OPC1 dose then set day to first day of month
- 4) If the AE start date is completely missing and the corresponding stop date is completely missing, the AE start date will remain missing.

A topline summary of treatment emergent adverse events with the number of events, number of subjects, and percentage of subjects for each category below will be tabulated by cohort and overall:

- Any TEAE and SAE
- Subjects Reporting at least one TEAE or TE SAE that has severity Grade 3 or higher that is also related to AST-OPC1, injection procedure, or tacrolimus
- TEAE and SAE Severity: Grade 1/Mild, Grade 2/Moderate, Grade 3/Severe, Grade 4/Life Threatening/Disabling, Grade 5/Fatal
- Categories for TEAE and TE SAE with possible relationship to: AST-OPC1, injection procedure, tacrolimus

The following tables will be presented for the number and percentage of subjects by cohort and overall:

- TEAE by preferred term sorted by descending number of overall events
- TEAE by SOC, PT, and maximum severity*
- Treatment Emergent Adverse Events by System Organ Class, Preferred Term and Possible Relationship to AST-OPC1, Injection Procedure, and Tacrolimus Treatment emergent SAE by SOC, PT, and maximum severity*
- TEAE of special interest by SOC and PT, defined as Urinary Tract Infections, Spasticity, and Neuropathic Pain based on an adjudication of adverse events by the biostatistics, data management, clinical, and sponsor teams.

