1.4.2 Surgical Injection Procedures

AST-OPC1 is injected directly into the spinal cord during an open surgical procedure under general anesthesia. The procedure requires a posterior approach, laminectomy, and opening of the dura. These steps are common in intradural spinal cord operations, and have several known risks, including:

- anesthesia-associated risks
- compression of nerve roots
- CSF leak
- deep vein thrombosis and pulmonary embolus
- further tissue damage to the spinal cord
- hemorrhage and/or fluid collection in tissues between the incision site and the spinal cord
- infection (incision site, intraspinal/CNS, pneumonia, urinary tract)

- intraspinal hemorrhage
- pain
- spinal cord tethering

These risks will be minimized as much as possible by selecting participating sites with highly qualified spine surgeons and ensuring good perioperative care. In the previous thoracic study of AST-OPC1 (Geron Protocol CP35A007), there were no serious or unexpected adverse events related to the injection procedure. There were 9 AEs in that study that were judged to be possibly related to the injection procedure. These were all Grade 1 or Grade 2 in severity and were predominantly transient postoperative pain, one brief, mild, elevated temperature, and one urinary tract infection.

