The target injection site is the caudal portion of the spinal cord injury epicenter and within a region of damaged but nonhemorrhagic spinal tissue. The target level and site should be confirmed by review of the baseline MRI scan and other radiological studies, as needed. For dose Cohorts 3 and 5, the two injections should both be in the caudal half of the lesion epicenter, if possible, and should be spaced at least several millimeters apart in both the lateral and rostral-caudal directions. If it is not possible to perform both injections in the caudal half of the lesion epicenter, then the second injection may be performed in the rostral half of the lesion epicenter.

Due to the migratory ability of the cells in AST-OPC1, targeting of the injection site does not need to be performed in a stereotactic fashion. However, the surgeon should ensure that the target site is sufficiently deep (at least 6–7 mm) within the spinal cord to minimize the chance of AST-OPC1 efflux.

Once the target spinal level is exposed, direct visualization of the spinal cord surface at the target level should be obtained by laminotomy or laminectomy and opening of the dura. When the dura is opened, CSF will efflux and will not typically continue to flow over the posterior surface of the spinal cord. If needed, gentle aspiration may be used to prevent CSF from flowing directly over the injection site while the dura is open. The spinal cord target site should be confirmed by direct or endoscopic visualization and by intraoperative ultrasound (if available and of sufficient quality).

The syringe positioning device is then set up and a syringe/needle assembly containing AST-OPC1 is loaded. The syringe positioning device is then used to advance the needle tip to the target injection site within the spinal cord.

If the surgeon observes substantial deformation of the spinal cord at the onset of attempted needle penetration, the surgeon may elect to raise the needle, use a scalpel to make a small (~1 mm) longitudinal incision of the pia at the intended penetration site, and then reattempt to insert the needle using the syringe positioning device.

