If spinal cord motion is deemed to be a problem, the surgeon will consult with the anesthesiologist, who may adjust the ventilator settings to decrease tidal volume and increase respiratory rate to minimize spine motion. If the surgeon deems that spinal motion will still interfere with delivery of AST-OPC1, ventilation can be suspended for several minutes while the needle is in the spinal cord.

Once the needle is at the target position, the surgeon will inject the AST-OPC1 dose over a period of 2 minutes. The surgeon should observe the needle entry site during injection using a surgical microscope or magnifying loupes to monitor for possible efflux of AST-OPC1, which would appear as an opaque liquid on the spinal cord surface. If efflux from the spinal cord is noted at the beginning of injection, the surgeon may consider advancing the needle deeper into the spinal cord. If efflux is still noted or if it occurs after a delay but prior to delivery of the specified volume, the surgeon should stop injection and record the amount delivered. The surgeon may then consider repositioning the needle a few millimeters caudal to the initial site and making an additional attempt to complete injection. However, the total volume of AST-OPC1 delivered to the spinal cord cannot be increased. In the previous clinical study of AST-OPC1 in thoracic SCI, efflux was not observed during the injection in any of the 5 subjects.

The injection needle is left in place for 1 additional minute following injection and then withdrawn using the syringe positioning device. If ventilator settings were altered during injection, normal ventilation should be resumed immediately after needle withdrawal. The surgical procedure is then completed according to the usual standard procedures.

If the surgeon determines that completion of the injection in any location may cause an unacceptable safety risk to the subject, the entire volume may not be delivered. The location(s) and volume(s) of AST-OPC1 actually delivered should be recorded in the eCRF.

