7.3 Injection Day (Surgery for AST-OPC1 Administration)

Vital signs

- CSF sample by lumbar puncture during pre-op or after induction of general anesthesia but prior to AST-OPC1 injection (~10 mL for white blood cell count, glucose, total protein, oligoclonal banding, myelin basic protein, and IgG index)
- AST-OPC1 Injection
- Begin tacrolimus administration 6 to 12 hours following AST-OPC1 injection
- Concomitant medications
- Adverse events

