9.3.1 Safety Analyses

All reported adverse events will be coded to a preferred term and classified by System Organ Class using the current version of MedDRA. Adverse events will be listed by subject and will include preferred term, verbatim term, severity, seriousness, relationship, action taken, and outcome. Relationship will address attribution to the investigational product (AST-OPC1), the surgical procedure, and/or the immunosuppressive agent. Tabulations will be prepared for all adverse events, related events, Grade 3 and higher events, and serous events. Designated adverse events of special interest will be tabulated separately as appropriate.

Summary statistics of individual clinical laboratory parameters will be prepared by time period. Shift tables comparing baseline versus most abnormal value will be generated for selected analytes with standard toxicity grades. For selected laboratory analytes, the frequency of abnormal values and/or the incidence of Grades 3 and 4 values may be tabulated if appropriate.

Clinically significant changes in physical examination findings and ECGs will be presented descriptively. Vital signs will be summarized and listed by subject. Findings from immunological assessments will be presented appropriately.

Concomitant medications will be coded to generic term using the World Health Organization Drug Dictionary and will be tabulated across subjects and listed by subject.

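### SAP 6.2.2 starts treatment emergence at cell delivery, so a timed, non-worsening procedure-related event from earlier in the same operation would be listed but left out of the relatedness tables

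*SAP*

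**What the plan says.** SAP 4.1 makes safety the primary endpoint. It names the cells, the injection procedure and the immunosuppression as the things to be observed, and lists the incidence, severity and relatedness of adverse events. It sets no treatment-emergent limit.

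SAP 6.2.2 then defines a treatment-emergent event as "any adverse event that starts on or after the date and time of the AST-OPC1 injection". The one exception is an earlier event that worsens after the product is given. All adverse events from consent onward go into listings. In SAP 9.1, all six adverse event tables for the All Treated Population are titled treatment emergent. The only planned table of events before treatment, 14.3.1.1.2, is for the Not Treated Population.

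Protocol 6.4 sets out the order of the operation. Under general anaesthesia, "direct visualization of the spinal cord surface at the target level should be obtained by laminotomy or laminectomy and opening of the dura". The syringe positioning device is then set up and the needle advanced, and only after that: "Once the needle is at the target position, the surgeon will inject the AST-OPC1 dose over a period of 2 minutes". Protocol 1.4.2 includes "anesthesia-associated risks" among the known risks of the surgical injection procedure. Protocol 9.3.1 describes attribution in the same terms: "Relationship will address attribution to the investigational product (AST-OPC1), the surgical procedure, and/or the immunosuppressive agent".

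**The concern.** The SAP's event window opens part-way through a procedure whose safety it sets out to measure. Anaesthesia, exposure and dural opening happen only because the cells are to be injected, yet an event that arises during them has its onset before the cut-off.

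The protocol itself foresees an event of this kind. Section 6.4 suggests considering an arterial line so that autonomic dysreflexia during surgery can be detected and managed quickly. If such an episode were judged procedure-related and resolved before the needle was placed, no relatedness table would show it.

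Two neighbouring cases are handled differently. If an anaesthetic event led to the injection being abandoned, it would be summarised in Table 14.3.1.1.2; if the subject went on to be injected, the same event would only be listed. And the partial-date rules in SAP 6.2.2 (2a and 3a(i), and rule 1 unless the stop date is also missing) move an uncertain onset to the dose date, apparently so that it counts, while an exact time before delivery is excluded.

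No hypothesis is tested (SAP 5.2), so the descriptive tables are the primary result. The risk is that they show no procedure-related event when one happened in the operating room.

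**Working it through.** **Denominator.** SAP 3.2.1 gives cohort sizes of 3, 6, 6, 6 and 4. Their sum is 3 + 6 + 6 + 6 + 4 = 25, which matches the stated number treated.

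**Applying the rule.** Take a treated subject with an event that starts after induction and before cell delivery, has a recorded time, is judged related to the injection procedure, and does not worsen.

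| Output | Is the event shown? |
|---|---|
| Adverse event listings (and serious event listings, if serious) | Yes |
| Table 14.3.1.1.1, rows by relationship (worded TEAE and TE SAE) | No |
| Table 14.3.1.1.1, related Grade 3 or higher row (worded TEAE or TE SAE) | No |
| Table 14.3.1.1.1, any-event and severity rows (worded TEAE and SAE) | Not if non-serious; unclear if serious, because SAE lacks the TE prefix |
| Tables 14.3.1.2, 14.3.1.3 and 14.3.1.4 | No |
| Table 14.3.2.1 (if serious), Table 14.3.2.2 (if of special interest) | No |
| Table 14.3.1.1.2 | No; Not Treated Population only |

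**Size per omitted event.**

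- The topline table counts events as well as subjects, so its procedure-related event count is 1 too low.
- Procedure-related incidence changes only if the subject has no other counted procedure-related event. It then falls by 1/25 = 4.0 points overall. Within a cohort, one subject is 1/3 = 33.3 points (Cohort 1), 1/6 = 16.7 points (Cohorts 2 to 4) or 1/4 = 25.0 points (Cohort 5).
- As an illustration with exact (Clopper-Pearson) 95% intervals, which the SAP does not plan for adverse events: 0/25 = 0% (0 to 13.7%) would be reported where 1/25 = 4.0% (0.1 to 20.4%) occurred. The upper limit for 0/25 is 1 − 0.025^(1/25) = 0.137.

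The documents give no rate for events in this interval, so these are effects per event and not an expected total.

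**The case against.** The strongest reply is that the gap may be empty. It exists only if onset clock times are collected, and the case report form casebook is not among the documents. The imputation rules work on dates alone, and Study Day (SAP 4.4.1) is a difference of dates. If only dates are held, an Injection Day event falls on the dose date and may be counted. This stands as a condition on the finding, although the SAP's own rule does refer to time.

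The available evidence also points to few such events. Protocol 3.1.2 expects surgical complications to show themselves almost always in the days after the operation. For the earlier thoracic study, Protocol 1.4.2 reports: "There were 9 AEs in that study that were judged to be possibly related to the injection procedure". A reader might use those 9 events in 5 subjects to size the loss. The documents do not support that: Protocol 1.4.2 calls them predominantly postoperative pain, and Section 1.3.2.2 describes the possibly related events as postoperative symptoms. None is described as starting before delivery.

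Other stronger readings also fail:

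- *Lumbar puncture complications are lost from the endpoint.* Protocol 7.3 does place before delivery the "CSF sample by lumbar puncture during pre-op or after induction of general anesthesia but prior to AST-OPC1 injection". But the puncture collects fluid for monitoring (Section 7.14.8) and is not a described step of the injection procedure.
- *Severity tables for procedure-related events are wrong.* Tables 14.3.1.4 and 14.3.2.1 are not split by relationship. The only planned row combining relationship and severity pools cells, procedure and tacrolimus at Grade 3 or higher.
- *Serious events disappear from every table.* Two topline rows may still count them.
- *The SAP breaches the protocol.* Protocol 9.3.1 says: "Tabulations will be prepared for all adverse events, related events, Grade 3 and higher events, and serous events". But SAP Section 2 gives the SAP precedence over the protocol's statistical section. The synopsis window of 365 days from injection can also be read as starting at injection.

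What remains is the SAP's rule set against the SAP's own primary endpoint. Listings and narratives would let a careful reader find the event, but they do not summarise incidence.

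**Conclusion.** The point holds in a limited form. By its stated rule, SAP 6.2.2 can omit from every relatedness summary a procedure-related event that begins during anaesthesia, exposure or dural opening and does not worsen after delivery. This rests on two conditions: that onset times are recorded, and that such an event occurs. Neither can be confirmed from the documents, and the likely number is very small.

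The loss is one event in the topline count each time, and 4.0 points of overall incidence only when it is the subject's sole counted procedure-related event. It is not evidence that procedure-related harm will be materially understated. It is worth correcting because it touches the primary endpoint and the change is cheap.

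**What to change.** In SAP 6.2.2, define a treatment-emergent event as one that starts on or after the start of the injection procedure on Injection Day, taken as induction of anaesthesia, or that worsens afterwards. If either the induction time or the event's onset time is not recorded, compare dates, so that an event dated on Injection Day counts. This also settles the status of untimed and imputed onsets.

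Apply the definition to every adverse event whatever its relationship, and to all six tables (14.3.1.1.1, 14.3.1.2, 14.3.1.3, 14.3.1.4, 14.3.2.1 and 14.3.2.2), with a footnote. Changing only procedure-related events, or only some tables, would give related and unrelated events different windows and make totals disagree.

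Add one topline row restricted to events starting after cell delivery, so that the narrower reading of the synopsis window is reported too.

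The cost is SAP wording, one derived flag, one table row and a footnote. No new adverse event collection is needed, since events are already collected from consent. Reported rates may become slightly less favourable, and a few unrelated Injection Day events from before delivery would also be counted.

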4. STUDY ENDPOINTS AND DEFINITIONS

4.1 Primary Endpoints

The primary endpoint of this Phase 1/2a study is safety and includes observations related to AST-OPC1 cells, the injection procedure, and the protocol-specified immunosuppression regimen. They include:

- Incidence, severity and relatedness of adverse events
- Changes in laboratory variables
- Changes at the injection site as monitored by MRI

Definitions relating to AEs and serious adverse events (SAE) are given in Section 10 of the protocol.

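### The onset-date imputation rules in SAP 6.2.2 can flag as treatment-emergent an adverse event that its own recorded dates place before injection: rules 1, 2a and 3a(i) ignore the stop date, and rule 2b does not say which year to impute

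*SAP*

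**What the plan says.** SAP 5.3 gives the imputation its purpose: "Missing or incomplete dates will be imputed per Section 6.2.2 for the purposes of determining treatment emergence". Under SAP 6.2.2 an AE is a TEAE if it starts on or after injection, or "if an adverse event that started before the AST-OPC1 injection worsened after the administration of the investigational product". AE collection begins at consent, so pre-injection events are in the data.

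The rules that matter here are:

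- Rule 1: "If onset date is completely missing, then onset date is set to date of first dose".
- Rule 2a, only the onset year known: "If year = year of AST-OPC1 dose, then set date to AST-OPC1 dose date".
- Rule 2b, only the onset year known and earlier than the dose year: where "medication AE end month and year are available, then set to first of the AE end month".
- Rule 2c, the fallback to 2b: "Otherwise if year < year of AST-OPC1 dose, then set month and day to December 31st".
- Rule 3a(i), only the day missing and the year equal to the dose year: "If month = month of AST-OPC1 dose then set day to day of AST-OPC1 dose date".
- Rule 4 leaves the start date missing, but only when start and stop are both completely missing.

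SAP 4.1 lists "Incidence, severity and relatedness of adverse events" first among the primary endpoints. In SAP 9.1, every AE summary table for the All Treated Population is a TEAE table.

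**The concern.** There are two separate faults.

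First, using the dose date is a sensible worst-case default when timing is unknown. When the stop date lies before injection, timing is not unknown: the event was over. Rules 1, 2a and 3a(i) never look at that date, and rule 4 does not help because it needs both dates to be absent. Rule 3a(i) is the most realistic route, since only the day has to be missing.

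Second, rule 2b is reached only when the recorded year already shows a pre-injection start. Such an event should be a TEAE only through worsening. The rule ties onset to the end month and applies no cap at the recorded year or at injection. Its neighbours 2c and 3b keep such an event pre-injection, so on the end-year reading a known end date makes the classification worse. The stray word *medication* suggests text carried over from another rule.

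At stake are the all-causality TEAE counts in cohorts of 3 to 6 subjects. The population has frequent background events: SAP 6.2.2 names urinary tract infection, spasticity and neuropathic pain as events of special interest, and Protocol 1.4.1 lists urinary tract infection, spasticity and pain as expected complications of the injury.

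**Working it through.** The plan gives no figure to reproduce, so the rules were applied as written to example records. The rules impute a date without a time, so an onset on the dose date is taken as meeting the on-or-after criterion.

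| Rule | Recorded onset | Recorded stop | Injection | Imputed onset | Flag |
|---|---|---|---|---|---|
| 1 | missing | 5 Jan 2017 | 10 Jan 2017 | 10 Jan 2017 | TEAE |
| 2a | 2017 | 28 Feb 2017 | 10 Mar 2017 | 10 Mar 2017 | TEAE |
| 3a(i) | Mar 2017 | 8 Mar 2017 | 10 Mar 2017 | 10 Mar 2017 | TEAE |
| 2b, end year used | 2016 | Mar 2017 | 10 Jan 2017 | 1 Mar 2017 | TEAE |
| 2b, onset year kept | 2016 | Mar 2017 | 10 Jan 2017 | 1 Mar 2016 | not TEAE |
| 2c | 2016 | none | 10 Jan 2017 | 31 Dec 2016 | not TEAE |
| 3b | Dec 2016 | Mar 2017 | 10 Jan 2017 | 1 Dec 2016 | not TEAE |

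In the first three rows the imputed onset falls after the recorded end (by 5, 10 and 2 days). In the fifth row the date precedes the injury itself, which can be at most 42 days before injection (Protocol 4.1).

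**When rule 2b misfires (end-year reading).** It does so when the end month is later than the dose month, or when the dose falls on the 1st of the end month. An event that ended before injection is never misflagged by this rule.

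**How many subjects rule 2b could reach.** The AE must begin after consent and in the calendar year before injection, so the consent-to-injection interval must cross a year end.

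- Subjects: 17 had been dosed when Amendment 3 was written (Protocol, Amendment 3 rationale), under a window of 14 to 30 days after injury (Protocol 1.3.3).
- Interval, low end: 3 days. Consent is required only before the screening tests, which may be done between Day -11 and Day -3 (Protocol 7 and 7.1).
- Interval, high end: 30 days, the upper limit of the earlier window.
- Assumption: injection dates are spread evenly over the year.
- Formula: subjects × interval / 365.
- Low: 17 × 3/365 = 0.14. High: 17 × 30/365 = 1.40.

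The other 25 − 17 = 8 subjects are assumed to have been injected by the end of 2017, since enrolment closed on 15 December 2017 (SAP 3.2.1). SAP 5.4 plans the interim for September 2018, with Cohorts 1–4 past Day 365. Taking 30 September 2018 and the 14-day visit window, 365 − 14 = 351 days earlier is 14 October 2017. So only the 4 Cohort 5 subjects could depart from that assumption.

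**How long the event must last.** For the 17, a year-end crossing puts the dose in January, so a wrong flag needs an end in February or later. The shortest such event runs from 31 December to 1 February, which is 32 days. The exception is a dose on 1 January, where 1 day suffices.

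**Effect of one wrong flag.** It adds 1 to the event count. It moves a subject row by at most 1/25 = 4.0 points overall, or in a cohort by 1/6 = 16.7, 1/4 = 25.0 or 1/3 = 33.3 points, and only if that subject has no other event in the row.

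**Check of the repair.** The rules and the repair were run over every 2017 injection date, with onsets from Day 0 to Day 364 at weekly steps, seven durations and the partial-date patterns tested. No true post-injection onset was lost under rules 1, 2a and 3a(i). No provably pre-injection event stayed flagged under rules 1, 2a, 2b and 3a(i).

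**The case against.** The strongest objection concerns rule 2b. Its text does not say which year to use. Rules 2c and 2d set only month and day and keep the recorded year; read the same way, 2b gives no false TEAE. This stands. The end-year reading is more natural, because the condition asks for the end month and year, but the text does not compel it. A reader might infer that rule 2b certainly creates false TEAEs, and the SAP does not support that. What is certain is that the rule is incomplete, and that it gives a wrong flag on one reading and an implausible date on the other. The fault in rules 1, 2a and 3a(i) does not depend on this.

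The data pattern should also be rare. AEs are to be entered promptly with their duration (Protocol 10.1) and source-verified (Protocol 11.4), so a stop date better known than the onset is unusual. This stands as a limit on size.

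The consequences are limited too. Analyses are descriptive, and over-counting is the conservative direction for safety. A reader might infer that the primary endpoint as worded in the protocol synopsis is inflated. That endpoint is related events, and Protocol 10.1.3 classes an event not reasonably related in time as unrelated, so an event over before injection should rarely enter a related row.

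Finally, AEs are listed by subject and outputs undergo quality control (SAP 6.2.2 and 7). This helps to trace an error, but nothing there overrides a flag that follows the rules as written.

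**Conclusion.** The point holds, and it is minor. Followed as written, rules 1, 2a and 3a(i) flag an AE with a recorded stop before injection as treatment-emergent, and no other passage corrects this. Rule 2b needs its year stated and a cap; whether it produces false TEAEs now depends on the reading.

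The size cannot be fixed, because the number of partial dates is not given. The error can only over-count, mainly in all-causality TEAE rows. The range of 0.14 to 1.4 subjects for rule 2b rests on even injection dates, an interval of 3 to 30 days, and the later 8 subjects having been injected by the end of 2017. A reader might take it as the number misclassified. It counts subjects whose interval could cross a year end. A wrong flag also needs a year-only onset, a known end month, no worsening and, unless the dose is on 1 January, an event of at least 32 days.

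**What to change.** Amend SAP 6.2.2 in two places.

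1. Rules 1, 2a and 3a(i): if the latest date the stop field allows is before the injection date, the AE is not treatment-emergent. That latest date is the stop date itself, the last day of a month-year stop, or 31 December of a year-only stop. Otherwise keep the dose-date default.
2. Rule 2b: delete *medication*, state that the end year is used, and set onset to the earlier of the first of the AE end month and 31 December of the recorded onset year. The AE is then a TEAE only if it worsened after injection.

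Leave rules 2c, 2d, 3a(ii) and 3b unchanged. With these changes, the first four rows of the table become non-TEAE, the rule 2b case with an imputed onset of 31 December 2016 and absent any worsening.

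The cost is a few lines of text and one derivation to reprogram. TEAE counts can only stay the same or fall.
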